### **2.3 Compliance Statement**

This study will be conducted in compliance with Good Clinical Practice (GCP), including the International Conference on Harmonisation (ICH) Guidelines and FDA regulations, consistent with the principles outlined in the Declaration of Helsinki. In addition, the Investigator agrees to adhere to all applicable local laws and regulatory requirements relevant to the use of new therapeutic agents.

The study will be conducted in compliance with the protocol. The appropriate Institutional Review Boards (IRBs) must approve the protocol, any amendments, and the subject informed consent form (ICF) prior to implementation.

Freely given written informed consent must be obtained from every subject prior to participation in this clinical trial. As part of this procedure, the Investigator must explain orally and in writing the nature, duration, and purpose of the study, and the action of the drug in such a manner that the study subject is aware of the potential risks, inconveniences, or AEs that may occur. The study subject should be informed that he/she is free to withdraw from the study at any time. He/she will receive all information that is required by federal regulations and ICH guidelines. The Investigator or designee will provide the Sponsor with a copy of the IRB-approved informed consent form prior to the start of the study. The rights, safety, and well-being of participating subjects are the most important considerations and should prevail over interests of science and society.

Study personnel involved in conducting this trial will be qualified by education, training, and experience to perform their respective task(s). This trial will not use the services of study personnel where sanctions have been invoked or where there has been scientific misconduct or fraud (e.g., loss of medical licensure, debarment).

### 3 STUDY OBJECTIVES

#### 3.1 Primary Objective

The primary objective of this study is to evaluate the safety and tolerability of 5 once-weekly IV infusions of SYNT001 at different dose levels in subjects with chronic pemphigus (vulgaris or foliaceus).

#### 3.2 Secondary Objectives

The secondary objectives of this study are as follow:

- To determine the PK of SYNT001 following 5 once-weekly 1-hour IV infusions at different dose levels
- To assess the effect of 5 once-weekly doses of SYNT001 at different dose levels on the following PD biomarkers:
  - Immunoglobulins: IgG, IgG subtypes (IgG1-4), IgA, IgM
  - Albumin
- To assess the effect of 5 once-weekly doses of SYNT001 at different dose levels on the following disease activity markers:
  - Serum anti-desmoglein (Dsg) (1 and 3) antibody levels
  - Pemphigus Disease Area Index (PDAI)
- To assess immunogenicity (anti-SYNT001 antibodies)

#### 3.3 Exploratory Objectives

The exploratory objectives of this study are as follow:

- To assess the effect of 5 once-weekly doses of SYNT001 at different dose levels on the following biomarkers, including:
  - Serum anti-epithelial cell antibody (AECA) levels by indirect immunofluorescence
  - Circulating immune complexes (CIC)
  - Complement component 3 (C3)
  - Exploratory biomarkers (*FCGR2A* single nucleotide polymorphism-SNP, RNAseq, urine IgG)
  - Immune phenotyping by flow cytometry for CD3+CD4+ T, CD3+CD8+ T, monocytes, NK cells and B cells
  - SYNT001 levels in skin biopsies (optional)
- To characterize corticosteroid use during the study

## 4 STUDY DESIGN

### 4.1 Study Sites

This study will be conducted at approximately 10 sites in the United States (US).

### 4.2 Study Endpoints

**Primary Outcome Measures:** Assessment of safety data (adverse events [AEs], serious adverse events [SAEs], vital sign measurements, ECGs and clinical laboratory tests) will be the primary safety measure.

### Secondary Outcome Measures

Pharmacokinetics:

- Half-life ( $t_{1/2}$ ), maximum plasma concentration determined directly from the concentration-time profile ( $C_{max}$ ), observed time to reach peak plasma concentration ( $T_{max}$ ), area under the plasma concentration-time curve from pre-dose (time 0) to 24 hours post-dose ( $AUC_{0-24}$ ), and area under the plasma concentration-time curve from pre-dose (time 0) to infinity ( $AUC_{0-\infty}$ )

PD Biomarkers:

- Ig Assessments: Serial assessments of total IgG and IgG subtypes (IgG1-4)
  - Serial assessments of total IgG and IgG subtypes (IgG1-4)
  - IgA levels
  - IgM levels
- Albumin levels

Disease activity markers:

- Serum anti-desmoglein (Dsg) (1 and 3) antibody levels
- Pemphigus Disease Area Index (PDAI) scores

Immunogenicity:

- Anti-SYNT001 antibodies

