Objective	Endpoint																								
Primary																									
Safety and tolerability of 5 once-weekly IV infusions of SYNT001 to subjects with pemphigus vulgaris or foliaceus	AEs and clinical (safety) laboratory tests																								
Secondary																									
PK of SYNT001 following a 1-hour IV infusion	PK parameters: $t_{1/2}$ , $C_{max}$ , $T_{max}$ , $AUC_{0-24}$ , and $AUC_{0-\infty}$ .																								
Effect of 5 once-weekly IV doses of SYNT001 on: 
 
Total IgG (IgG1-4), IgA, IgM, and albumin
 
Serum anti-Dsg (1 and 3) antibodies
 
	Changes in levels of IgG, IgG subtypes (IgG1-4), IgA, IgM, albumin, serum anti-Dsg (1 and 3) antibodies																								
Assess immunogenicity	Anti-SYNT001 antibodies																								
Disease Activity	PDAI Scores																								
Exploratory																									
Effect of 5 once-weekly IV doses of SYNT001 on biomarkers including: 
 
CIC
 
C3
 
Serum anti-epithelial cell antibody (AECA) levels
 
Exploratory biomarkers (FCGR2A SNP, RNAseq, urine IgG)
 
Immune phenotyping by flow cytometry
 
	Changes in CIC; C3; AECA levels by indirect immunofluorescence; FCGR2A SNP; RNAseq; urine IgG, CD3 + CD4 + T, CD3 + CD8 + T, monocytes, NK cells and B cells; urine IgG levels; changes in blood transcriptome																								
Concomitant Treatment	Corticosteroid use during the study																								
SYNT001 levels in skin biopsies	Measures of SYNT001 levels in skin biopsies																								

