**Table 2: Timing Window Allowances for PK/PD Sampling, ECG, and Vital Sign Measurements**

Pharmacokinetic and Pharmacodynamic Sampling	
Timepoint	Tolerance Window
0 hour	-240 min to 0 hour
5 minutes post end-of-infusion	± 5 minutes
2, 4, & 6 hours post end-of-infusion	± 15 minutes
24 hours post end-of-infusion	± 60 minutes
48 hours post end-of-infusion	± 120 minutes
ECG	
Timepoint	Tolerance Window
5 minutes post end-of-infusion	± 10 minutes
Vital Signsa	
Timepoint	Tolerance Window
0 hour	-240 min to 0 hour
15, 30, and 45 minutes after start of infusion	± 5 minutes
60 minutes after start of infusion	± 10 minutes
30, 60 and 120 minutes post end-of-infusion	± 10 minutes

a: Vital signs to include blood pressure, pulse rate, respiratory rate, oral temperature, and pulse oximetry.

---

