## 2 BACKGROUND AND RATIONALE

SYNT001, a humanized, affinity-matured IgG4-kappa monoclonal antibody (mAb), blocks IgG and IgG immune complex (IC) interactions with the neonatal Fc receptor (FcRn) and thereby the major functions of FcRn in protecting IgG and IgG ICs from degradation and their role in downstream signaling events. Specific and high affinity blockade of FcRn with SYNT001 has been shown to increase the catabolism of IgG and IgG IC in healthy volunteers. This predicts that SYNT001 will also accelerate degradation of endogenous circulating IgG autoantibodies and IgG-antigen IC specifically involved in the pathogenesis of autoimmunity. Blocking FcRn interactions with IgG-containing ICs further predicts that SYNT001 will have consequences for innate and adaptive cellular immunity. In the first instance, blocking multimeric IgG IC interactions with FcRn within antigen-presenting cells will result in inhibition of IC-stimulated inflammatory cytokine production and release by these cells. In addition, as FcRn determines the intracellular itinerary of IgG ICs within and among compartments important in cellular immunity, it is anticipated that SYNT001 will block antigen processing and presentation of antigens contained within IC that otherwise lead to CD8+ and CD4+ T cell activation. Thus, SYNT001 will specifically target immune functions associated with IgG that are involved in certain autoimmune conditions and dismantle their ability to cause disease.

SYNT001 targets key mechanisms contributing to pathology in a variety of IgG-mediated autoimmune disorders, including warm antibody autoimmune hemolytic anemia (WAIHA), pemphigus, and chronic inflammatory demyelinating polyneuropathy (CIDP).

While current treatments for certain autoimmune disorders, including high-dose steroids, immunosuppressants, intravenous immunoglobulin (IVIG), plasmapheresis, and anti-CD20 monoclonal antibodies (mAbs), such as rituximab, can be effective, they are associated with significant adverse effects, as well as delayed or non-durable responses.

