#### **6.7.4 Pharmacokinetics (PK) Sampling**

Starting on Days 0 and 28, serum samples will be collected just prior to the start of study drug infusion (pre-dose), at 5 minutes and 2, 4, 6, 24, and 48 hours after the end-of-study drug infusion. Additional samples will be collected on Days 5 and 33. The actual time and date of each blood draw is to be recorded.

Study drug concentration will be used to calculate the following PK parameters:  $t_{1/2}$ ,  $C_{max}$ ,  $T_{max}$ ,  $AUC_{0-24}$ , and  $AUC_{0-\infty}$ .

Detailed instructions for sample collection and preparation will be provided in a separate laboratory manual

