**Table 4: Pharmacodynamic/ Activity Assessments**

Parameter	Collection Timepoints

 
IgG, IgG subtypes (IgG1-4), IgA, IgM
 
	Screening, and Days 0, 1, 2, 5, 7, 12, 14, 19, 21, 28, 29, 30, 33, 42, and 56

 
Circulating immune complexes (CIC)
 
	Days 0, 5, 7, 12, 14, 19, 21, 28, 33, 42, and 56

 
Albumin
 
	Screening, and Days 0, 7, 14, 21, 28, 33, 42, and 56

 
Anti-Dsg (1 and 3) antibody titer
 
	Screening, Days 0, 7, 14, 33, and 56

 
Complement component 3 (C3)
 
Anti-epithelial cell antibody (AECA) levels by indirect immunofluorescence
 
	Days 0, 14, 33, and 56

 
Exploratory biomarker (RNAseq, Urine IgG)
 
	Days 0, 14, 33, and 56

 
Immune phenotyping by flow cytometry for measurement of CD3+CD4+ T, CD3+CD8+ T, monocytes, NK cells and B cells
 
	Days 0 and 28

 
Exploratory biomarker (FCGR2A SNP)
 
	Day 0

See [Table 2](#) for timing window allowances with respect to measurement collection.

Detailed instructions for sample collection (including collection tubes) and preparation will be provided in a separate laboratory manual.

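### SYNT001 is itself an IgG4 antibody, so the IgG4 secondary endpoint may include circulating drug, increasingly with dose, unless the assay is shown not to detect it

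*Protocol*

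**What the plan says.** Section 2 of the protocol introduces the drug: "SYNT001, a humanized, affinity-matured IgG4-kappa monoclonal antibody (mAb), blocks IgG and IgG immune complex (IC) interactions". Section 4.2 lists "Serial assessments of total IgG and IgG subtypes (IgG1-4" among the secondary outcomes. The synopsis gives the endpoint as "Changes in levels of IgG, IgG subtypes (IgG1-4), IgA, IgM, albumin, serum anti-Dsg (1 and 3) antibodies" and singles out no time point.

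Table 4 sets the immunoglobulin samples at "Screening, and Days 0, 1, 2, 5, 7, 12, 14, 19, 21, 28, 29, 30, 33, 42, and 56". Days 1 and 29 are the "24 hours post end-of-infusion" samples of Table 2, Days 2 and 30 the "48 hours post end-of-infusion" samples, and Days 5 and 33 fall 120 h after doses 1 and 5. On dosing days the sample is pre-dose, about 7 days after the previous infusion.

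Section 6.7.4 places the SYNT001 concentration samples: "Starting on Days 0 and 28, serum samples will be collected just prior to the start of study drug infusion (pre-dose", then through 48 h after the infusion and on Days 5 and 33. Drug concentration is therefore available at the same visits as the early immunoglobulin samples.

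Section 6.7 leaves the assays to unnamed methods at a central laboratory and refers to a laboratory manual. Section 12.6 says only that pharmacodynamic results are summarised by cohort. The protocol does not mention drug interference in these assays.

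**The concern.** An assay built to measure human IgG4 may also read an infused humanised IgG4 antibody. The measured value would then be the subject's own IgG4 plus drug. Under linear kinetics the drug part at a given time rises in proportion to dose: threefold from 10 to 30 mg/kg and 4.5-fold from 10 to 45 mg/kg. The drug would be adding to the quantity it is meant to lower, most of all in the highest cohort. A reader of the cohort summary could conclude that IgG4 is spared or rises at higher doses when it has fallen.

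**Working it through.** **The protocol's own IgG figures.** Section 9.6.2 uses 1150 mg/dL (mean) and 700 mg/dL (lower limit).
- 50% fall: 1150 x 0.5 = 575; 700 x 0.5 = 350 mg/dL.
- 80% fall: 1150 x 0.2 = 230; 700 x 0.2 = 140 mg/dL.

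All four match the text.

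**Inputs from the protocol:** doses of 10 and up to 30 mg/kg, optional third cohort up to 45 mg/kg; sampling at 24, 48 and 120 h; mean total IgG 1150 mg/dL.

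**Assumptions, not in the protocol:** distribution volume V 40-70 mL/kg; half-life 12-168 h; baseline IgG4 at 3-6% of total IgG, so 34.5-69 mg/dL; full detection of SYNT001 by the assay.

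**Drug level (mg/dL)** = dose / V x 100 x 2^(-t / half-life).

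Just after infusion: 10/70 x 100 = 14 to 10/40 x 100 = 25 at 10 mg/kg; 43-75 at 30 mg/kg; 64-113 at 45 mg/kg. The fraction left at 24 h is 0.25 (half-life 12 h) to 0.906 (168 h); at 48 h it is 0.0625 to 0.820.

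Example, 30 mg/kg at 24 h: the high end is 75 x 0.906 = 67.9 mg/dL, and 67.9/34.5 = 197% of baseline IgG4. The low end is 42.9 x 0.25 = 10.7 mg/dL, and 10.7/69 = 16%.

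| Dose (mg/kg) | Drug as % of baseline IgG4, 24 h | 48 h | Drug as points of baseline total IgG, 24 h | 48 h |
|---|---|---|---|---|
| 10 | 5-66 | 1-59 | 0.3-2.0 | 0.1-1.8 |
| 30 | 16-197 | 4-178 | 0.9-5.9 | 0.2-5.4 |
| 45 | 23-295 | 6-268 | 1.4-8.9 | 0.4-8.0 |

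At 120 h, 30 mg/kg adds from about 0 (half-life 12 h) to about 133% of baseline IgG4 (168 h), so Day 5 may or may not be affected.

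**What the reader would see.** Apparent change = -(true fall) + drug / baseline. The sign flips once drug as a share of baseline exceeds the true fall. As an illustration under a second set of assumptions, take V = 45 mL/kg (22, 67 and 100 mg/dL at the three doses), baseline IgG4 of 20-90 mg/dL and a true Day 1 fall of 20%:
- 30-80% of drug left, 10 mg/kg: -20% + 6.7/90 = -13%, to -20% + 17.8/20 = +69%.
- 30-80% left, 30 mg/kg: -20% + 20/90 = +2%, to -20% + 53.3/20 = +247%.
- 10% left: -18% to -9% at 10 mg/kg; -13% to +13% at 30 mg/kg.

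**Total IgG on Day 29**, true fall 75% (1150 to 287.5 mg/dL), 30-80% of the last dose left. Apparent fall = 1 - (287.5 + drug)/1150, which gives 74.4-73.5% at 10 mg/kg, 73.3-70.4% at 30 mg/kg and 72.4-68.0% at 45 mg/kg.

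**Limit of the formula.** It counts one dose only. At a half-life of 168 h, the four earlier weekly doses would multiply the Day 29 figures by 1 + 0.5 + 0.25 + 0.125 + 0.0625 = 1.94. At 12 h they add practically nothing.

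**The case against.** The strongest objection is that everything depends on whether the assay reads SYNT001, and the protocol neither states nor excludes this. Without detection every figure above is zero. A reader might infer that the endpoint does measure the infused drug; the documents support only that it may. This stands, and the point is conditional for that reason.

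Second, Section 12.6 does not commit the trial to uncorrected values, and Section 12.3 leaves detailed methods to the SAP, which was not available for this review. It is therefore too strong to say that the plan prescribes a wrong derivation. What remains is more than missing detail: the protocol fixes the analyte, the sampling times and a drug of the same subclass, so following it as written can give a dose-dependent false result.

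Third, the size is almost wholly assumed. The largest values combine the lowest baseline with the highest retention. That stands too.

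Fourth, a reader might infer that the total IgG dose-response could be reversed. The numbers do not support this. In the Day 29 illustration the distortion between the 10 and 30 mg/kg cohorts is about 1 to 3 points (74.4 against 73.3; 73.5 against 70.4).

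Fifth, a reader might infer that dose escalation would be misled. The dose escalation committee does review available and relevant pharmacodynamic data through Day 42 (Section 11.5). However, no passage ties escalation to IgG4 or to 24-48 h values, and the stopping rule rests on adverse events.

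Finally, subtracting drug concentration works only where concentration is measured, so a corrected series would be incomplete. The fix has to say so.

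**Conclusion.** The point holds in conditional form, with medium confidence. SYNT001 is an IgG4 antibody, IgG4 is a named secondary endpoint, and several samples fall when drug may still be circulating. Unless the assay is shown not to detect SYNT001, the IgG4 results may include drug, more so at higher doses.

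With detection and the stated assumptions, the added amount at 24-48 h could equal or exceed baseline IgG4 at 30-45 mg/kg, enough to mask a fall or produce a false rise. With fast elimination it could be only a few percent by 48 h. For total IgG the single-dose addition is small, at most about 2, 6 and 9 percentage points of baseline at 10, 30 and 45 mg/kg. Total IgG can remain the main measure.

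**What to change.** In Sections 6.7.5 and 12.6:

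1. Have the central laboratory run a spike-recovery check of SYNT001 in the IgG4 and total IgG assays.
2. If SYNT001 is detected, report IgG4 at the visits with a drug concentration (Days 1, 2, 5, 28 pre-dose, 29, 30 and 33) as measured IgG4 minus recovery x same-visit SYNT001 concentration, all in mg/dL. Do the same for total IgG as a sensitivity analysis.
3. Flag IgG4 at visits without a drug concentration (Days 7, 12, 14, 19, 21, 42 and 56) as uncorrected. Days 12 and 19 matter most here: they are 5 days post-dose, like Day 5.
4. Add IgG1+IgG2+IgG3 by cohort as a supportive summary that is free of drug by subclass, alongside total IgG and not in its place.
5. If SYNT001 is not detected, state that and drop the correction.

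The cost is one laboratory check and some derivation and table wording. No extra samples are needed. The downside is that corrected values also carry the error of the drug concentration assay.

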### Exploratory Outcome Measures

Biomarkers, including:

- CIC
- C3
- Serum AECA levels
- Exploratory biomarkers (*FCGR2A* SNP, RNAseq, urine IgG)

- Immune phenotyping by flow cytometry for measurement of CD3+CD4+ T, CD3+CD8+ T, monocytes, NK cells and B cells
- SYNT001 levels in skin biopsies (optional)

#### Concomitant Treatments

- Corticosteroid use

Further details on the statistical and analytical plan for these endpoints are available in [Section 12](#), Statistical Considerations.

### 4.3 Overview of Study Design

This will be a multicenter, open-label study to assess the safety, tolerability, activity, PK, PD, and immunogenicity of 5 once-weekly IV infusions of SYNT001 to subjects with chronic pemphigus (*vulgaris* or *foliaceus*).

Planned doses of SYNT001 to be studied are 10 mg/kg and up to 30 mg/kg. Two cohorts of 8 eligible subjects each will receive 5 once-weekly 60-minute infusions of SYNT001 10 mg/kg or up to 30 mg/kg. Based on review of safety, PD, and clinical outcomes of the first cohort, the dose for the second cohort may be adjusted, but with a maximum dose of 30 mg/kg. Based on review of safety, PD and clinical outcomes from these 2 cohorts, a third cohort of up to 8 subjects may be treated at another dose, with a maximum dose of 45 mg/kg, but may also be lower than 10 mg/kg or between 10 and 30 mg/kg, inclusive.

Cohort	No. of Subjects	Dose
1	8	SYNT001 10 mg/kg
2	8	SYNT001 30 mg/kg

Cohorts will be dosed sequentially beginning with Cohort 1. The first 2 subjects will be dosed at least 24 hours apart. A review of the 24-hour safety data for the first subject will be performed to ensure that there are no overt safety concerns before dosing the second subject. A review of the 7-day safety data for the first 2 subjects will be performed prior to dosing the remaining 6 subjects in the cohort. This evaluation will include a review of AE/SAE reports, vital sign assessments, physical examinations, ECGs and clinical laboratory testing. The seriousness, severity, and relatedness of AEs/SAEs will also be considered in the safety evaluation. Safety data will be reviewed on a continuous basis throughout the study. All data through Day 42

(2 weeks after the last subject's last dose in Cohort 1) will be reviewed before Cohort 2 is initiated. Cohort 2 and Cohort 3, if added, will be dosed per the same schedule.

Safety evaluations will be conducted by a dose escalation committee (DEC). The DEC will consist of the Medical Monitor, an Independent Clinical Expert and a Syntimmune Medical Officer. To assist in the safety assessments, the DEC may request that Investigators, other experts, or members within their organizations review the data and participate in the discussions. Dosing and dose escalation will proceed if the DEC has determined that it would be safe and appropriate to do so. In addition, over the course of the study, the DEC will review any drug-related SAEs to determine if modifications to the study or other measures are necessary to ensure the safety of the subjects.

On days where study drug is administered, vital sign and pulse oximetry measurements will be collected immediately prior to the infusion; 15, 30, and 45 minutes after the start of the infusion; at completion of the infusion; and 30 minutes, 1 hour and 2 hours following completion of the infusion.

On Days 0 and 28, PK blood samples will be collected prior to infusion start and then over the subsequent 48 hours. Subjects will remain at the clinic through the 6-hour PK sample collection and will return to the clinic for the 24- and 48-hour collections. Additional samples will be collected on Days 5 and 33.

On Day 0 photographs will be taken of active lesions. Follow-up photographs will be taken of the same areas on Days 33 and 56. If a subject begins a steroid taper, additional photographs will be taken at the clinic visit during which the decision to begin the taper is made.

Subsequent visits will occur on Days 1, 2, 5, 7, 12, 14, 19, 21, 28, 29, 30, 33, and 42 for safety assessments, study drug dosing, sample collections, and other study procedures.

Subjects also will return to the clinic on Day 56 (28 days after receiving their last dose of study drug) for an End-of-Study/Follow-Up visit.

See [Table 1](#) for a schedule of all study events. To assess safety and tolerability, subjects will undergo physical examinations (PEs; including weight), vital sign measurements, clinical (safety) laboratory tests, AE assessments, concomitant medication assessments, and electrocardiograms (ECG).

**Note:** No vaccinations may be given from within 2 weeks of screening until 2 months following the last dose of study drug.

#### **4.4 Randomization and Blinding**

This is an open-label study.

## 5 STUDY POPULATION

### 5.1 Target Population

This study will be conducted in approximately 16 male and female subjects (2 cohorts of 8 subjects each) with a confirmed diagnosis of pemphigus (vulgaris or foliaceus); however, a third cohort of up to 8 subjects may be added. Subjects will be enrolled only once in the study and will not be included in subsequent dosing cohorts. Subjects who withdraw for any reason other than an AE and who do not receive study drug or have only received one dose of study drug may be replaced, up to one subject per cohort. Subjects who do not receive all doses of study drug will continue to be followed through 28 days after their last dose. The maximum number of subjects who may be enrolled in this study is 27 (24 + up to 3 replacements, as necessary). Within each dosing cohort, no more than 3 subjects may be enrolled with pemphigus foliaceus.

